Subjects will be instructed to follow the visitor policy during each study visit. They will be given an Information Sheet about COVID-19 Related Risks through email prior to the visit. They will be instructed to come alone to the CRU, wear a face mask upon entry to the building, practice social distancing and hand hygiene. Study team will minimize face-to-face contact with the participants using all remote means possible during study visits. They will adhere to 6-foot distance between participants and staff or between staff and other staff whenever feasible. Staff will be trained to use a surgical or procedure mask with a face shield PPE at a minimum for all participant interaction. During a CPAP sleep study, Airborne and Contact Precautions with Eye Protection PPE will be used (isolation gown, double exam gloves, N95/Drager respirator with a face shield). The door of the patient room will be kept closed whenever possible during a CPAP sleep study.

Pre-sleep procedures. Subjects will undergo a brief history and physical examination. They will report to the clinical research unit and undergo anthropometric assessment including weight, height, neck, and waist circumference. A point of care screening test for hemoglobin will also be performed to exclude pre-existing anemia. Patients with a hemoglobin < 10 g/dL are ineligible for this study. At approximately 17:30, they will eat a standard dinner containing 30% fat, 50% carbohydrate, and 20% protein with kcal based upon the Mifflin-St Jeor formula. Two peripheral IV's will be placed for blood sampling during sleep, with one as a backup in case of failure of one IV. IV tubing will be extended to an adjacent control room so that blood samples can be obtained without disturbing the subject.

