Dual-energy X-ray absorptiometry (DEXA). After the baseline glucose level for the OGTT has been drawn and the patient has consumed the glucose solution, they will undergo a DEXA scan. The DEXA scan will be used to estimate fat mass, which will be one of the variables analyzed as a predictor of FFA elevation.

Subjects may eat breakfast after the OGTT testing is completed

To minimize the impact of sleep loss on driving safety, subjects are asked to either (1) arrange for an alternate means of transportation home (this is mentioned on the consent or to (2) sleep as needed for up to 4 additional hours before discharge.

Repeat sleep testing:

Repeat sleep tests may be requested from the subject under the following circumstances:

- (1) A technical problem with data acquisition including PSG lead failure/artifacts, incomplete blood collection from IV insertion or maintenance problems.
- (2) Poor sleep efficiency <50% of time in bed

If the initial sleep study meets these criteria and a repeat test is deemed necessary by the PI, then the repeat testing will be scheduled at least 1 week following the initial study.

Scoring. Sleep will be scored according to Rechtschaffen and Kales criteria. Respiratory events will be scored according to AASM criteria. Apneas will be considered present when there is no air flow for >10 seconds. Obstructive apneas will be considered present when apneas are associated with positive strain gauge deflections indicating thoracic movement. Apneas will be considered central in origin when cessation of air flow is not accompanied by thoracic movement as measured by the strain gauge. Mixed apneas will be defined by episodes of no air movement resulting from central apnea followed by obstruction. Hypopneas will be scored for reductions in airflow of 30% lasting >10 seconds accompanied by either an arousal or fall in oxyhemoglobin saturation of 3% or greater.

Data Analysis and Anticipated Outcomes:

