The primary outcomes is nocturnal plasma FFA levels. The main independent variable is OSA versus CPAP exposure during sleep. Since FFA are measured multiple times per subject per night, we will perform mixed linear model analysis using condition as a fixed factor and subject ID as a random factor. Sleep physiology that is measured on a continuous basis will be condensed into 30 minute bins to create a parallel data structure with metabolic parameters. As a secondary analysis, we will also examine whether there are patient-specific (“static”) determinants of FFA level during sleep such as age, sex, or body mass index and whether these variables interact with sleep (“dynamic”) variables such as OSA severity. We hypothesize that OSA exposure increases FFA, compared to CPAP. We will then examine whether sleep physiology (e.g. AHI, arousals, heart rate) is dynamically associated with FFA, and whether urine catecholamine levels are associated with increases in FFA. For variables measured once (RHI, morning lipid profile) or averaged (e.g. nocturnal FFA level) we will perform one-way ANOVA for comparisons. We will also compare sleep physiology between the 3 nights, examining variables such as apnea hypopnea index, metrics of hypoxia, and sleep architecture/duration. Data analysis will be performed with a biostatistician and described under the “Study Statistics” section.

b. Study duration and number of study visits required of research participants.

Each study subject will make two overnight visits to the sleep lab. Subjects will be screened with an initial telephone interview. During this screening, only information necessary to assess eligibility for the study will be collected, or information voluntarily provided by the patient to initiate or maintain correspondence. Subjects without any of the self-reported exclusionary criteria will be scheduled for a face-to-face visit for further screening. At this visit, eligibility for

participation in the study protocols will be confirmed. Urine screening for pregnancy in women of child-bearing age will also be performed.

c. Blinding, including justification for blinding or not blinding the trial, if applicable.

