We will include adults of all races ≥ 20 and ≤ 75 years old, with a history of mild to severe OSA (AHI or RDI > 10). They must also own a CPAP machine and report the ability to tolerate sleeping with or without CPAP during the night.

Exclusion Criteria:

1. Uncontrolled hypertension with systolic blood pressure > 170 or diastolic blood pressure > 110
2. Congestive heart failure
3. Use of, clonidine, or nicotinic acid medication
4. Diabetes requiring the use of insulin
5. Pregnancy, by urine testing in women of child-bearing age

6. Patients with a prior history of falling asleep while driving, involved in a near-miss or motor vehicle accident, or and those in high-risk occupations such as commercial drivers or pilots.
7. Hemoglobin < 10 g/dL on point of care screening.

6. Drugs/ Substances/ Devices

- a. The rationale for choosing the drug and dose or for choosing the device to be used.

During CPAP withdrawal nights (both at home and in the lab) we will use NDS as a CPAP placebo. NDS may improve snoring but have no treatment value for OSA[6]. By including NDS as a placebo, we will avoid potential confounding such as anxiety caused by stopping CPAP.

- b. Justification and safety information if non-FDA approved drugs without an IND will be administered.
N/A

Study Statistics

The overall analysis plan has been presented in section 4, “Data Analysis and Anticipated Outcomes”. In this section we briefly address the statistical methods to be used for analysis separated by specific aim:

Specific Aim 1: To examine whether OSA, elicited by CPAP withdrawal, causes lipolysis and cardio-metabolic dysfunction.

Primary outcome: FFA level, comparing between CPAP and OSA nights, analyzed using linear mixed effect models.
Independent variable: CPAP/OSA exposure.

Specific Aim 2: To examine factors associated with lipolysis during sleep.

Primary outcome: FFA level

Independent variables: OSA severity (AHI, arousal index, heart rate, urine catecholamines), Patient factors (age, sex, body mass index/fat distribution).

These analyses are primarily designed to understand the heterogeneity of lipolysis during CPAP withdrawal.

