- *Sex-specific effects:* This will be assessed by (1) comparing mean change in FFA level during CPAP withdrawal between men and women (unpaired T-test); (2) modeling mean FFA level as a function of sex (as well as sex x BMI interactions) in multivariable regression. We hypothesize that men will exhibit greater OSA-induced FFA elevation than women, with or without adjustment for OSA severity and fat distribution.
- *Effects of OSA severity or sympathetic activation:* We will apply linear mixed models with FFA as the outcome, OSA severity or SNS variables (e.g. AHI, ODI, arousal index, HR, urine catecholamines) as fixed factors and subject ID as the random effects variable. Iterative time lags will be used to account for potential delayed effects of dynamic variables. We hypothesize that plasma FFA level will be independently associated with AHI, arousals from sleep, HR elevation, or urine catecholamine level.
- *Identification of robust “responders”:* We will examine FFA elevation as a dichotomous outcome, defining “FFA responders” as those who exhibit Δ FFA $\geq 10\%$ during CPAP withdrawal (subject to change depending on the distribution of responses; the 10% threshold is based on a median increase in nocturnal FFA of $\sim 8.9\%$ in our preliminary data). OSA severity, sleep architecture, sex, age, and fat mass will be compared between responders and non-responders.
- *Identification of potential “downstream” effects of FFA elevation.* We will test the association between nocturnal FFA profile and other cardiometabolic outcomes (e.g. morning OGTT, endothelial function). Multivariable regression will be used to adjust for potential confounders such as age, sex, and BMI.
- *Identification of potential circulating genetic/epigenetic changes.* An exploratory aim of this study is to examine effects of CPAP withdrawal on peripheral blood mononuclear cell (PBMC) gene expression. We will utilize real-time polymerase chain reaction (RT-PCR) arrays (Qiagen MAP Kinase RT2 Profiler and Human Toll-Like Receptor (TLR) Signaling Pathway RT2 Profiler PCR Arrays, Qiagen, Valencia, CA) to characterize gene changes that result from nocturnal hypoxemia.

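### The only multivariable sex model has FFA level rather than FFA change as its outcome, so the adjusted half of the sex hypothesis has no matching test

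*Combined protocol and SAP*

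**What the plan says.** The sex-specific effects bullet (Study Statistics, Specific Aim 2) lists two analyses. Item (1) is an unpaired t-test comparing men and women on mean change in FFA during CPAP withdrawal. Item (2) is "modeling mean FFA level as a function of sex (as well as sex x BMI interactions) in multivariable regression". The bullet then states its hypothesis: "We hypothesize that men will exhibit greater OSA-induced FFA elevation than women, with or without adjustment for OSA severity and fat distribution".

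Other parts of the plan bear on this:

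- The Specific Aim 2 header gives the outcome as FFA level, yet describes the purpose this way: "These analyses are primarily designed to understand the heterogeneity of lipolysis during CPAP withdrawal".
- Data Analysis and Anticipated Outcomes (section 4) plans a secondary analysis of "determinants of FFA level during sleep such as age, sex, or body mass index", and of whether these factors interact with dynamic variables such as OSA severity.
- The responder bullet dichotomises the FFA rise: "OSA severity, sleep architecture, sex, age, and fat mass will be compared between responders and non-responders".
- The DEXA paragraph says: "The DEXA scan will be used to estimate fat mass, which will be one of the variables analyzed as a predictor of FFA elevation".
- The Sample Size paragraph bases the trial on the sex difference in FFA elevation, that is, on change.

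**The concern.** The hypothesis concerns a response, meaning how much FFA rises when CPAP is removed. It is stated twice, once without and once with adjustment. A t-test cannot adjust, so within the bullet only item (2) could serve the adjusted half, and its outcome is level.

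Men and women may differ in FFA on CPAP for reasons unrelated to OSA. If item (2)'s sex coefficient is read as the adjusted test, such a difference would pass for a difference in response. An opposite gap could dilute or cancel a real one. The trial would then have no pre-specified way to say whether a sex difference found by the t-test persists at equal OSA severity and fat. That question follows directly from the comparison on which the sample size rests.

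**Working it through.** **Inputs from the Sample Size paragraph.** Change in FFA is 0.047 ± 0.04 mmol/l in men and 0.021 ± 0.04 in women. The plan asks for 80% power at 0.05, giving 78 evaluable (39 + 39), and 92 enrolled after 15% loss.

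**Reproducing the plan's figures.** The difference is 0.047 - 0.021 = 0.026, so d = 0.026/0.04 = 0.65. A two-sided two-sample t-test needs 38.14 per group, hence 39 + 39 = 78, with 80.9% power at that size. Enrolment is 78/0.85 = 91.8, rounded up to 92. Both figures match and both rest on change.

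**What item (2) estimates.** Let g be the men-minus-women difference on the CPAP night and r the difference in change. Withdrawal-night level equals CPAP-night level plus change, and least squares is linear in the outcome. With the same regressors, the sex coefficients therefore add:

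- outcome withdrawal-night level: g + r
- outcome mean of both nights: g + r/2
- outcome change: r

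With r = 0.026:

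| g (assumed) | Withdrawal night | Both nights | Change |
|---|---|---|---|
| -0.026 | 0.000 | -0.013 | 0.026 |
| 0 | 0.026 | 0.013 | 0.026 |
| +0.026 | 0.052 | 0.039 | 0.026 |

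**Illustrative rejection rates.** The documents give neither g nor the between-subject SD of level, so these rates are assumptions and not estimates for this trial. The simulation used 10,000 trials per scenario with 39 + 39 subjects and terms for sex, centred BMI and their product. BMI was assumed to have mean 33 and SD 6 and to be unrelated to FFA. CPAP-night level was independent of change. Each range covers a withdrawal-night level SD of 0.10 to 0.15.

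| Truth | Withdrawal night | Both nights | Change |
|---|---|---|---|
| r = 0.026, g = 0 | 12–21% | 7–9% | 80% |
| r = 0, g = 0.026 | 12–20% | 12–22% | 5% |
| r = 0, g = 0.05 | 30–58% | 31–64% | 5% |

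An exact calculation without covariates for the first row, withdrawal night, gives 20.5% at SD 0.10 and 11.8% at SD 0.15.

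**Whether another planned analysis fills the gap.**

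- The section 4 interaction of static factors with OSA severity gives a sex difference in the slope of FFA on severity. It does not give the sex difference in change at equal severity and fat.
- The responder comparison uses change, but dichotomised and with no adjustment described.
- The DEXA paragraph makes fat mass a predictor of elevation, but does not put it in a model with sex and severity.
- The Aim 2 header lists the variables without specifying a model of change by sex.

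**The case against.** The strongest reply is that the section is brief by its own account and that item (2)'s list of terms is plainly incomplete. It omits OSA severity and fat distribution, which the hypothesis mentions. A sex-by-night term or CPAP-night FFA might also have been intended, and either could direct the model at the response. This is possible, but neither is stated. The same sentence specifies change for item (1) and level for item (2), and the Aim 2 header also says level. If change was meant, the text should say so.

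A second reply is that the rejection rates depend on BMI being centred, which the plan does not mention. With BMI uncentred, item (2) rejects in only about 5–7% of trials when there is no response difference, and its power for a true 0.026 falls to about 5%. This limits the false-positive illustration. It does not rescue the model: the expected coefficient is still g + 0.026 under the same assumptions, and the test becomes nearly uninformative.

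Third, the section 4 interaction comes near the question, the harm arises only if item (2) is read as the adjusted test, and the powered t-test is intact. These points stand as limits on severity. The level model is also legitimate as a description of what determines FFA level, since level is a declared Aim 2 outcome.

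**Conclusion.** The concern holds. As written, the plan states an adjusted hypothesis about response and supplies no model of change to test it. The one multivariable sex model mixes the CPAP-night sex gap with all or half of the response difference. That result is algebra and needs no assumed SD. How much it would mislead in practice depends on g and the SD of level, neither of which the documents give, so the rejection rates above are illustrations. The t-test on change and the 78/92 sample size are not affected. This should be fixed, but it does not threaten the powered comparison.

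**What to change.** Keep item (2) as a description of the determinants of FFA level, and state that its sex coefficient is not a test of the sex hypothesis. Add the adjusted test: regress each subject's change in night-mean FFA (nasal-strip night minus CPAP night) on sex, off-CPAP AHI, mean-centred BMI, DEXA fat mass (amount) and waist circumference (distribution). Report the sex coefficient with its 95% CI from this model without sex × BMI, and put sex × centred BMI in a second model. A mixed model would serve equally well if it contained sex × night and the night interaction of each adjusting covariate.

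Label the adjusted test supportive of item (1), and state that the 80% power belongs to the unadjusted t-test only.

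**Cost.** This changes wording only. AHI and DEXA fat mass are already planned, and BMI and waist come from the "anthropometric assessment including weight, height, neck, and waist circumference". Enrolment need not change if the test is labelled supportive.

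**Downside to state.** Power may be below 80% at 78 evaluable. With four covariates (72 degrees of freedom), the variance is inflated by 1/(1 - R²), where R² is the share of the variance of sex that they explain. If they explain none of the outcome and the adjusted difference is 0.026:

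| R² (assumed) | Power at 78 | Evaluable for 80% |
|---|---|---|
| 10% | 77% | 86 |
| 20% | 72% | 96 |
| 30% | 66% | 110 |
| 40% | 59% | 126 |
| 50% | 52% | 152 |

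If covariates also predict the change, the adjusted difference itself moves. Take one covariate with share R of both the sex variance and the within-sex outcome variance, and hold the unadjusted difference at 0.026. The shift is √(R/(1-R)/0.25) × √R × 0.04. At R = 0.1 this is 0.0084, so the adjusted difference is 0.018 (power 48%) or 0.034 (96%). At R = 0.2 it is 0.0179, giving 0.008 (14%) or 0.044 (over 99%). No single power figure should be claimed for the adjusted test.

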We hypothesize that patient specific and sleep-specific factors influence nocturnal lipolysis. Patient factors may include age, sex, or body mass index (BMI). Sleep-specific factors may include OSA severity and/or OSA-induced sympathetic activation, elapsed time, or sleep stage. Additional outcomes of interest are effects of OSA, CPAP on circulating genetic/epigenetic changes.

3. Background (briefly describe pre-clinical and clinical data, current experience with procedures, drug or device, and any other relevant information to justify the research)

OSA induces repetitive upper airway closure during sleep, and affects 24% of middle aged men and 9% of women in the United States[3]. Several studies suggest that OSA may induce cardio-metabolic complications such as insulin resistance, endothelial dysfunction, and dyslipidemia[4] culminating in cardiovascular disease and death[5]. Unfortunately, it remains unclear what mediates detrimental outcomes in OSA. We have shown that OSA causes rapid FFA elevations during sleep in heart failure subjects, which can be prevented by supplemental oxygen [1]. We speculate that stimulation of the sympathetic nervous system by OSA and intermittent hypoxia cause lipolysis, leading to excessive FFA mobilization from adipose tissue.

It is not known whether OSA causes surges of FFA in non-CHF patients, and whether CPAP can abolish the increase. It is also unclear which patient-related or sleep apnea features predict nocturnal FFA elevations, and

whether FFA elevations from OSA are associated acutely with detrimental physiologic changes. In subjects with a history of OSA, we will examine nocturnal FFA in the presence or absence of therapeutic CPAP. We hypothesize that CPAP withdrawal leads to increases in nocturnal FFA. We will also determine whether morning endothelial function and glucose tolerance correlate with nocturnal FFA changes.

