PSG setup. On each study night from 22:40 until 06:40, a PSG will be performed. The sleep study will include electroencephalography, electrooculography, oxygenation, respiratory effort, CPAP airflow, and transcutaneous CO₂ monitoring. Respiratory effort will be measured by thoraco-abdominal movement assessed by mercury strain gauges. Surface electrodes will be placed at C₃A₂ and C₃O₁, a submental electrode, and left and right electro-oculogram will be used to stage sleep. Electrocardiograph (EKG) tracings will be recorded from three chest electrodes. Continuous measurement of oxygen saturation will be recorded using an ear oximeter (model No 472-1A, Hewlett Packard, Waltham, Mass). Transcutaneous CO₂ will be monitored using a Radiometer TCM-4 device. Signals from the electroencephalograph, EKG, electromyogram, electrooculogram, respiratory strain gauge, ear oximeter and thermistors will be recorded on a computer with RemLogic software.

During the CPAP night, patients will sleep using CPAP set to their prescribed home CPAP settings. Airflow will be recorded with a pneumotachograph in the CPAP circuit. CPAP pressure will be titrated if necessary to prevent

obstructive hypopneas and apneas. During NDS nights, ClearPassage® strips will be applied at bedtime. Flow will be measured using a nasal cannula and oral thermistor.

[figure not shown]
Blood work and urine collection

All samples will be obtained via the indwelling IV, without awakening the subject. Blood samples will be drawn at 30 to 60 minute intervals beginning at 5:30 PM and continuing until the next morning at 6:30 AM as shown in the figure below. At 10:30 PM, when the sleep study starts, blood is sampled at 30 minute intervals in order to capture dynamic changes in FFA metabolism during sleep. Each blood sample will be 4 cc in volume and placed into lavender top tubes (EDTA) for centrifugation to obtain plasma. Cells are removed from plasma by centrifugation for 10 minutes at 1500 x using a refrigerated centrifuge. If necessary, based on nursing schedules, the timing of sampling and sleep procedures can be shifted up to 1 hour later or earlier.

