Following centrifugation, plasma will be transferred to cryovials for storage. The final morning sample at time of awakening (6:30 AM) will be 12 cc (3 tubes) since we plan additional assays with this sample (lipid panel, inflammatory markers) and 4 cc will be retained as whole blood for future potential analysis. In patients that have signed the optional consent for isolation of genetic material, we will collect an additional 16 cc (4 tubes) at 6:30 AM since this volume is required for isolation of peripheral mononuclear cells. In total, the blood collected will be approximately 174 cc. For patients that consent to isolation of genetic material, the total will be 190 cc. This quantity is much less than during a blood donation. Samples will be frozen at -80°C for research pertaining to metabolic effects of OSA, with the consent of participants. A morning urine sample will be collected for measurement of catecholamines.

Morning procedures:

The PSG montage will be disconnected. One IV is removed, leaving the other IV in place for use during later glucose tolerance test. Then peripheral artery tonometry, DEXA scanning, and OGTT will be performed as follows:

Peripheral arterial tonometry (EndoPAT). The subject will be in the supine position. A blood pressure cuff is placed on the non-dominant arm while the contralateral arm is used for control comparisons. Baseline measurements will be taken for 5 minutes, during 5-min occlusion of the brachial artery by inflation of the automated cuff 50 mmHg above systolic blood pressure, and for 5 minutes upon release of the cuff. Endothelium-mediated vasodilation is assessed using a finger pulse wave amplifier. The reactive hyperemia index (RHI) and the augmentation index (AI) will be derived by software and used as metrics of endothelial function and arterial stiffness respectively.

Oral glucose tolerance test (OGTT). From the indwelling antecubital IV, baseline insulin (gold top tube, 4 cc) and glucose (grey top tube, 4 cc) will be obtained. The patient will be given a 75 g glucose solution to drink within 5

minutes. Blood samples of insulin and glucose are then collected at 30, 60, 90, and 120 minutes after drinking the glucose solution. They will be asked, if possible, to remain awake during the OGTT.

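### The Aim 2 within-night FFA model omits time of night, serial correlation and a lag rule, so it can create or hide an association if FFA and a predictor both trend overnight

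*Combined protocol and SAP*

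**What the plan says.** Under Study Statistics, Specific Aim 2 (effects of OSA severity or sympathetic activation), FFA is the outcome of a linear mixed model. Variables such as AHI, ODI, arousal index and heart rate enter "as fixed factors and subject ID as the random effects variable. Iterative time lags will be used to account for potential delayed effects" of the dynamic variables. The stated hypothesis is that FFA is related to these variables in their own right.

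The data form a time series within each night. In section 4a (Blood work and urine collection), from the start of the sleep study "blood is sampled at 30 minute intervals in order to capture dynamic changes in FFA metabolism during sleep". In section 4a (Data Analysis and Anticipated Outcomes), "Sleep physiology that is measured on a continuous basis will be condensed into 30 minute bins to create a parallel data structure" with the metabolic measures.

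Time is recognised elsewhere. Section 2, Specific Aim 2, says: "Sleep-specific factors may include OSA severity and/or OSA-induced sympathetic activation, elapsed time, or sleep stage". Section 4a (Pre-sleep procedures) standardises the evening meal: "At approximately 17:30, they will eat a standard dinner containing 30% fat, 50% carbohydrate, and 20% protein". Yet the list of Aim 2 independent variables contains OSA severity and patient factors only. The section 4a model also has no time term: "we will perform mixed linear model analysis using condition as a fixed factor and subject ID as a random factor". Neither section gives a residual correlation structure, robust standard errors, a set of lags, a rule for selecting among them or multiplicity control.

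**The concern.** A subject random intercept removes differences in level between subjects. It does not remove a trend that all subjects share over the night. Dinner is at about the same time for everyone, so time since the meal runs in step with time of night, and any FFA trend tied to it is shared. If AHI, arousals or heart rate also trend, the fitted slope takes up the product of the two trends. It is biased upward if they move together, downward if they move apart, and not at all if the predictor is flat.

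Two further gaps act on their own. With a subject intercept alone, neighbouring half-hour residuals are treated as independent. If both series are autocorrelated, the standard errors are too small. And if several lags are tried and the best is reported, the false-positive rate rises even when there is neither trend nor autocorrelation.

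At stake is the reading of the Aim 2 slopes: a significant one might reflect a common time course, and a null one might conceal a real link.

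**Working it through.** **The plan's own figures.** The plan gives no figure for this model. Its sample size, for the comparison of men and women, reproduces: difference 0.047 − 0.021 = 0.026, SD 0.04, d = 0.65; the t-based size is 38.14 per group, rounded up to 39, so 78; 78/0.85 = 91.8, so 92. It is used here only to set n = 78.

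**Inputs.** From the documents: 78 subjects, and samples every 30 minutes from 22:30 to 06:30, so 8 × 2 + 1 = 17 per night. Assumed, because the documents give no overnight profile: within-night FFA SD 0.15 mmol/l, within-night AHI SD 15/h, linear drifts, one (withdrawal) night, two-sided 5% tests. There is no true link unless stated.

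**Shared trend.** A straight line of total height 1 over 17 equally spaced points has variance v = 2(1² + … + 8²)/(17 × 16²) = 408/4352 = 0.09375. With FFA drift f and AHI drift a, the expected slope without a time term is

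b = f·a·v / (15² × 16/17 + a²·v).

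For f = 0.1 and a = 10, b = 0.09375/(211.76 + 9.375) = 0.00042 mmol/l per event/h. The standard error is about 0.15/√(78 × 17 × 221.14) = 0.000277, so z = 1.53 and the rejection rate is about P(Z > 1.96 − 1.53) = 33%. Simulation (2,000 datasets per setting) gives 32%. The formula runs somewhat high at larger drifts, because the unmodelled FFA trend also inflates the residual variance. Simulated false-positive rates with independent residuals:

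| AHI drift | FFA drift 0.05 | 0.1 | 0.2 |
|---|---|---|---|
| 0 | about 5% | about 5% | about 5% |
| 2/h | 5% | 6% | 10% |
| 5/h | 6% | 12% | 29% |
| 10/h | 12% | 32% | 79% |

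**Hiding a real link.** Take a true slope of 0.0008 mmol/l per event/h, which has 80% power when time bins are in the model. If AHI falls by 10/h while FFA rises by 0.1, the expected slope is 0.0008 − 0.00042 = 0.00038, z is about 1.36, and power is about P(Z > 0.60) = 27%, as in simulation. At FFA drift 0.2 the expected slope is 0.0008 − 0.00085, slightly below zero.

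**Serial correlation.** When both series are AR(1) with the same ρ, the large-sample variance of the slope is (1 + ρ²)/(1 − ρ²) times the model-based one. At ρ = 0.5 this is 1.25/0.75 = 1.67, so the standard error is too small by a factor of 1.29 and the rejection rate is 2P(Z > 1.96/1.29) = 13%. Simulation with a flat AHI gives 11–14%. At ρ = 0.3 the effect is modest: 6–8% with time bins and uncorrected errors.

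**Lag search.** For independent tests, the best of 3 lags gives 1 − 0.95³ = 14.3% and the best of 5 gives 1 − 0.95⁵ = 22.6%. Simulation with no drift and no autocorrelation gives 15% and 22%.

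**Does the remedy work?** At ρ = 0.5, FFA drift 0.1 and AHI drift 10/h, the model as written gives 42%, clustered errors alone 26%, time bins alone 10%, and both together 5%. Across the drift and correlation settings, time bins with clustered errors give about 5–7% at a single lag.

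**The case against.** The strongest reply is that this is brevity and not a wrong choice. Study Statistics says that it treats methods briefly, analysis is to be done with a biostatistician, and elapsed time is already named under Aim 2. A reader might infer that the plan rejects a time term; it does not. What remains is that a concrete model is written down, and followed literally it has these faults.

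Second, nothing in the documents shows that AHI trends overnight. That stands. The larger rates depend on an AHI drift of 10/h, and at 2/h the harm is slight. A reader might conclude that a significant slope can never be told apart from a common time course. That holds only if both series trend.

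Third, adjusting for time can remove real signal. If OSA's effect accumulates over the night, time of night is partly a marker of that effect. In one run (AHI drift 10/h, 0.0002 mmol/l per cumulative event/h), rejection fell from 53% to 6% once time bins were added, although the unadjusted result was itself non-specific. This stands, and it is why both estimates should be shown.

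Fourth, a reader might object that catecholamines are listed with the half-hourly predictors although "A morning urine sample will be collected for measurement of catecholamines". That is not a fault. Lags are applied only to dynamic variables, only continuously measured physiology is binned, and a once-per-night covariate is legitimate in a random-intercept model.

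Finally, the stakes are limited: this is Aim 2 of a pilot.

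**Conclusion.** The point holds for the within-night Aim 2 associations and should be corrected. The omissions are in the current text. Their consequence is conditional: bias needs a trend in both FFA and the predictor, understated errors need autocorrelation in both, and inflation from lags needs a search without control. The false-positive rates, from about 5% to 79% under the shared trends considered, 11–14% under AR(1) of 0.5 and about 22% for the best of five lags, rest on assumed drifts, SDs and correlations and are not predictions for this trial.

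A reader might extend this to the main comparison. The documents do not support that: Aim 1 contrasts two nights sampled over the same hours, so a time course common to both balances out. The sample size rests on the change in FFA in men versus women and is unaffected.

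**What to change.** In the Aim 2 model for OSA severity and sympathetic activation:

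- Add elapsed time of night, as 30-minute bins or a spline. Elapsed time is preferable to clock time, because "the timing of sampling and sleep procedures can be shifted up to 1 hour later or earlier".
- Use AR(1)-type residuals or subject-clustered standard errors. Both this and the time term are needed.
- Report each estimate with and without the time term.
- Name a small set of lags with multiplicity control, or label lag results exploratory.
- State which nights enter. The stated purpose of Aim 2 points to the withdrawal night; if both nights are pooled, keep condition in the model, as in section 4a.

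The cost is plan wording, a little more analysis and some power. With a real bin-level link and no FFA drift, time bins cost about 3 points of power at AHI drift 10/h and about 6 to 12 points at 20 to 30/h; more is lost if the effect accumulates. At AR(1) of 0.5, clustered errors give 60–62% power, against a nominal 74–76% with uncorrected errors whose false-positive rate is 10–12%. AR(1) residuals give about 80% if that structure is right. No further subjects, visits or samples are needed.
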